8.4.2 Method of Detecting AEs, SAEs, and Other Reportable Safety Events

Care will be taken not to introduce bias when detecting AEs and/or SAEs and other reportable safety events. Open-ended and nonleading verbal questioning of the participant is the preferred method to inquire about AE occurrence.

8.4.3 Follow-up of AE, SAE, and Other Reportable Safety Event Information

After the initial AE/SAE report, the investigator is required to proactively follow each participant at subsequent visits/contacts. All AEs, SAEs, and other reportable safety events, including pregnancy and exposure during breastfeeding, events of clinical interest (ECIs), cancer, and overdose will be followed until resolution, stabilization, until the event is otherwise explained, or the participant is lost to follow-up (as defined in Section 7.3). In addition, the investigator will make every attempt to follow all nonserious AEs that occur in randomized participants for outcome. Further information on follow-up procedures is given in Appendix 3.

8.4.4 Regulatory Reporting Requirements for SAE

Prompt notification (within 24 hours) by the investigator to the Sponsor of SAE is essential so that legal obligations and ethical responsibilities towards the safety of participants and the safety of a study intervention under clinical investigation are met.

The Sponsor has a legal responsibility to notify both the local regulatory authority and other regulatory agencies about the safety of a study intervention under clinical investigation. The Sponsor will comply with country-specific regulatory requirements and global laws and regulations relating to safety reporting to regulatory authorities, IRB/IECs, and investigators.

Investigator safety reports must be prepared for suspected unexpected serious adverse reactions (SUSARs) according to local regulatory requirements and Sponsor policy and forwarded to investigators as necessary.

An investigator who receives an investigator safety report describing an SAE or other specific safety information (eg, summary or listing of SAE) from the Sponsor will file it along with the IB and will notify the IRB/IEC, if appropriate according to local requirements.

8.4.5 Pregnancy and Exposure During Breastfeeding

Although pregnancy and infant exposure during breastfeeding are not considered AEs, any pregnancy or infant exposure during breastfeeding in a participant (spontaneously reported to the investigator or their designee), including the pregnancy of a male participant's female partner, that occurs during the study are reportable to the Sponsor.

All reported pregnancies must be followed to the completion/termination of the pregnancy. Pregnancy outcomes of spontaneous abortion, missed abortion, benign hydatidiform mole, blighted ovum, fetal death, intrauterine death, miscarriage, and stillbirth must be reported as serious events (Important Medical Events). If the pregnancy continues to term, the outcome (health of infant) must also be reported.

8.4.6 Disease-related Events and/or Disease-related Outcomes Not Qualifying as AEs or SAEs

Efficacy endpoints as outlined in this section will not be reported to the Sponsor as described in Section 9.4.1.

Specifically, the suspected/actual events covered in this exception include any event that is disease progression of the cancer under study.

The Sponsor will monitor unblinded aggregated efficacy endpoint events and safety data to ensure the safety of the participants in the study. Any suspected endpoint that upon review is not progression of the cancer under study will be forwarded to Global Pharmacovigilance as an SAE within 24 hours of determination that the event is not progression of the cancer under study.

8.4.7 Events of Clinical Interest (ECIs)

Selected nonserious and SAEs are also known as ECIs and must be reported to the Sponsor.

Events of clinical interest for this study include:

1. An overdose of Sponsor's product, as defined in Section 8.5, that is not associated with clinical symptoms or abnormal laboratory results.
2. Hepatic ECIs include any of the following events if the events are considered not due to disease progression as judged by the investigator. All of these events (if not associated with disease progression under study) will require holding study treatment, notification of the event(s) to the Sponsor within 24 hours after awareness via electronic media or paper.

For dose interval modification, refer to Section 6.6.1. For guidance related to the diagnosis and management of hepatic ECIs, refer to Section 6.6.2.

- ALT:
 - Among subjects with Baseline ALT $<2 \times \text{ULN}$: ALT $\geq 5 \times \text{ULN}$
 - Among subjects with Baseline ALT $\geq 2 \times \text{ULN}$: ALT $>3 \times$ the Baseline level
 - ALT >500 U/L regardless of baseline level
- Total Bilirubin:
 - Total bilirubin >3.0 mg/dL
- Regardless of laboratory values, hepatic decompensation diagnosed clinically, including:
 - New onset clinically detectable ascites requiring intervention for >3 days

- Hepatic Encephalopathy
- Gastrointestinal bleeding

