Investigators will assess disease recurrence radiographically (with site radiologist) during study intervention and efficacy follow-up. Disease recurrence will be documented by the investigator radiographically (with site radiologist) and will be verified by BICR prior to discontinuation of study intervention. Disease recurrence can also be confirmed with pathology if required per the site's standard of care. For participants who discontinue for reasons other than BICR-verified extrahepatic disease recurrence or confirmed with pathology if required per the site's standard of care, imaging should continue to be performed as if on study intervention until extrahepatic disease recurrence has either been verified by BICR or confirmed with pathology if required per the site's standard of care.

Disease recurrence can be intrahepatic or extrahepatic:

- Intrahepatic disease recurrence will be defined as the appearance of one or more intrahepatic lesions with a longest diameter of at least 10 mm and a typical vascular pattern of HCC on triphasic CT scan or MRI of the abdomen (ie, hypervascularization in the arterial phase with washout in the portal venous or late venous phase). Intrahepatic lesions larger than 10 mm that do not show a typical vascular pattern may be diagnosed as HCC by evidence of a growth interval of at least 10 mm in ≥ 4 weeks after the initial scan showing disease recurrence. Both de novo liver tumors and intrahepatic metastases will be considered intrahepatic disease recurrence.

- Extrahepatic disease recurrence will be defined as the appearance of one or more unequivocal new extra-nodal lesions or malignant enlargement of a previously normal lymph node. If a potential new extra-nodal lesion is equivocal, for example because of small size or clinical presentation, continued follow-up will show whether it truly represents disease recurrence. If it is later confirmed as disease recurrence, it should be retrospectively assigned at the visit where it was first seen. A lymph node ≥ 15 mm in short axis is presumed to represent disease recurrence. A lymph node 10-14 mm in short axis may represent disease recurrence, with reviewers using additional information (such as location, morphological signs and change in size) to inform their clinical judgment to determine whether it represents disease recurrence. Participants will also be discontinued from study intervention if they have ascites or pleural effusion deemed to be malignant.

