Note: After the investigator determines absence of radiologic disease, expedited verification of absence of radiologic evidence of disease will be performed by BICR at Screening and will be used to determine participant eligibility.

[figure not shown]
5. Has an ECOG performance status of 0 or 1 within 7 days prior to C1D1 (Appendix 9).
6. Has a Child-Pugh class A liver score (5 to 6 points) within 7 days prior to C1D1 (see Section 8.3.4).
7. Has AFP concentration lower than 400 ng/mL within 28 days prior to C1D1 (if there are several AFP values available within 28 days before C1D1, the closest AFP value to C1D1 should be below 400 ng/mL).

8. Has AFP concentration at initial diagnosis prior to resection or ablation available (if there are several AFP values available prior to resection or ablation, the closest AFP value to the date of resection or ablation should be entered in the eCRF).

Note: Participants without AFP concentration at initial diagnosis prior to resection or local ablation may be allowed to be randomized upon Sponsor consultation.

9. Participant may have a past or ongoing HCV infection. Participants must have completed their treatment at least 1 month prior to C1D1 or have received at least 1 month of DAA HCV therapy with no DAA-related safety events and stable LFTs. For participants not on anti-HCV therapy at the time of randomization, DAAs for treatment of HCV infection can be initiated per Investigator's discretion, if LFTs are stable after 3-6 months of study intervention upon Sponsor consultation. Refer to Appendix 7 for country-specific requirements.
10. Participant may have controlled hepatitis B, as long as they meet the following criteria:

-
-

Refer to Appendix 13 for hepatitis B definitions and treatment considerations.

11. Has recovered adequately from toxicity and/or complications from the local intervention (surgical resection or local ablation) prior to starting study intervention.

Demographics

12. Is male or female, at least 18 years of age at the time of signing the informed consent.

Female Participants

13. Contraceptive use by women should be consistent with local regulations regarding the methods of contraception for those participating in clinical studies.

A female participant is eligible to participate if she is not pregnant or breastfeeding, and at least one of the following conditions applies:

- Is not a woman of childbearing potential (WOCBP)

OR

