6.6.2 Guidance for Management of Hepatic Events of Clinical Interest

Hepatic ECIs (HECIs) have been described in Section 8.4.7. All of these HECIs will require holding study intervention and notification of the Sponsor within 24 hours. All cases of retreatment after interruption of study intervention for HECI must be reported to the Sponsor and recorded in the database.

Immediate assessment if HECI:

All Participants

- All participants should be considered for evaluation according to the directions below within 72 hours of the alert for a non-overdose ECI. For laboratory assessments of HECIs, central laboratory is preferred; local laboratory is acceptable if central laboratory is not available.
- Procedures:
 - Consider obtaining a consultation with a hepatologist
 - Obtain a workup for hepatitis if there is no underlying hepatitis, including hepatitis A, B, C, D, E, Epstein-Barr virus, and cytomegalovirus
 - Assess for ingestion of drugs/supplements with hepatotoxic potential
 - Assess for alcohol ingestion
 - Assess for potential bacterial infection, biliary obstruction, or occult gastrointestinal bleeding
 - Repeat ALT, AST, total bilirubin, direct bilirubin, alkaline phosphatase, glutamyl transpeptidase, international normalized ratio (INR), and complete blood count with differential
 - Measure HCV RNA viral load
 - HBV DNA, HbsAg, HbeAg, anti-HBc (total and IgM), anti-Hbe, and anti-HBs regardless of prior HBV status (Note: participants should be questioned about compliance with the use of antiviral agents)
 - Other laboratories or imaging studies as clinically indicated
 - Consider liver biopsy if indicated

HCC patients are at risk for a range of complications that can cause hepatic laboratory abnormalities with or without clinical decompensation. Those with a history of chronic HCV or HBV infection also have the potential to experience virologic flares. Immune-related hepatitis has been observed in approximately 1% of participants who received pembrolizumab. The following section provides further guidance on the diagnosis and management of potential hepatic complications among HCC participants in this study.

Management of HECI for Pembrolizumab/Placebo

	Diagnosis	Management

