Participants should continue treatment or continue in the Efficacy Follow-up Phase until disease recurrence has been verified by BICR or confirmed with pathology if required per the site’s standard of care. Exceptionally, if the investigator identifies disease recurrence that is not verified by BICR and the participant is clinically unstable or unable to continue study intervention due to rapid clinical deterioration, study intervention or continue in the Efficacy Follow-up Phase may be discontinued after consultation with the Sponsor.

Clinical instability is defined as the following:

- Symptoms and signs indicating clinically significant progression of disease
- Decline in ECOG performance status

- Requirements for intensified management, including increased analgesia, radiation or other palliative care

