Pregnancy/Lactation Exposure	Report if participant has been exposed to any protocol-specified intervention (eg, procedure, washout or run-in treatment including placebo run-in)	Report all	Previously reported – Follow to completion/termination; report outcome	Within 24 hours of learning of event
Event of Clinical Interest (require regulatory reporting)	Report if: - due to intervention - causes exclusion	Hepatic ECIs except those considered due to disease progression as judged by the investigator	Not required	Within 24 hours of learning of event
Event of Clinical Interest (do not require regulatory reporting)	Report if: - due to intervention - causes exclusion	Report - non-hepatic ECIs and those not requiring regulatory reporting	Not required	Within 5 calendar days of learning of event

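### An investigator's unverified attribution to progression removes a threshold-meeting liver event from the mandatory dose hold and 24-hour ECI notice

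*Combined protocol and SAP*

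**What the plan says.** Section 8.4.7 sets the hepatic thresholds: ALT at least 5×ULN (baseline below 2×ULN), ALT above 3× baseline (baseline 2×ULN or more), ALT above 500 U/L, total bilirubin above 3.0 mg/dL, or clinical decompensation. Meeting a threshold is not enough to enter the class: "Hepatic ECIs include any of the following events if the events are considered not due to disease progression as judged by the investigator". The next sentence attaches the consequences, with a differently worded condition: "All of these events (if not associated with disease progression under study) will require holding study treatment", together with notice to the Sponsor within 24 hours.

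Section 6.6.2 refers back to Section 8.4.7 for the definition and repeats the consequences: "All of these HECIs will require holding study intervention and notification of the Sponsor within 24 hours". Table 6 (Section 8.4.1) gives the reporting rule in a third wording: "Hepatic ECIs except those considered due to disease progression as judged by the investigator".

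Elsewhere the protocol has disease status checked centrally. At entry (Section 5.1, criterion 4), "expedited verification of absence of radiologic evidence of disease will be performed by BICR at Screening and will be used to determine participant eligibility". Under Section 4.1, recurrence "will be verified by BICR prior to discontinuation of study intervention". Section 8.2.1 sets the default while recurrence is unverified: "Participants should continue treatment or continue in the Efficacy Follow-up Phase until disease recurrence has been verified by BICR", with pathology as an alternative where the site's standard of care requires it.

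**The concern.** Participants start treatment with no detectable tumour, on a drug for which immune-related hepatitis is a recognised risk (Section 6.6.2). A marked ALT or bilirubin rise in this setting could be drug-related, viral, or an early sign of recurrence. Section 8.4.7 lets the investigator settle that question in favour of recurrence with no supporting evidence, and the settlement itself removes the hold and the ECI notice. The instruction that then applies is to keep treating until recurrence is verified.

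What is at stake is the care of an individual participant and how soon the Sponsor learns of the event. If the event is in fact immune-related hepatitis, dosing may continue with no protocol rule requiring a pause.

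**Working it through.** No figure in the plan is being tested. The check sets the provisions side by side and then counts doses on the calendar.

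**Step 1. What follows from each judgement when a threshold is met**

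| Investigator's view | Hepatic ECI under 8.4.7? | Required hold and 24-hour ECI notice? | Treatment default |
|---|---|---|---|
| Not due to progression | Yes | Yes (8.4.7, 6.6.2, Table 6) | Held |
| Due to progression, recurrence verified | No | No | Discontinued (7.1) |
| Due to progression, recurrence not verified | No | No | Continue (8.2.1) |
| Uncertain | Not covered expressly; read literally, not in the class | Unclear | Unclear |

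The third row is the gap. The fourth is loose drafting.

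**Step 2. Does another rule supply the hold in the third row?**

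- Table 4 (Section 6.6.1) covers non-hepatic immune-related events only.
- The hepatitis B and C rows in Section 6.6.2 have their own ALT triggers for interruption (above 5×ULN and/or above 3× baseline). They sit under the hepatic ECI management heading and concern viral disease.
- Section 6.6.2 asks for imaging to look for tumour progression when bilirubin is raised, but within hepatic ECI management. An event already attributed to progression does not clearly reach that step.
- Section 7.1 requires a stop if the investigator or Sponsor thinks the participant is at unnecessary risk. That is mandatory once the opinion is formed, but no threshold triggers it.
- The hepatic stops in Section 7.1 include ALT above 20×ULN, well above the 8.4.7 entry level. They are labelled hepatic ECIs without restating the exclusion, so their reach here is unclear.
- The clinical-instability route in Section 8.2.1 is optional and needs Sponsor consultation. An ALT rise without symptoms need not qualify.
- Section 8.4.6 sends a suspected endpoint to pharmacovigilance as an SAE once review shows it was not progression. The 24 hours run from that later determination, and no hold follows.
- Ordinary AE and SAE reporting continues, but it too turns on attribution (Sections 8.3.5, 8.4.6 and 10.3.2).

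None is a clear mandatory hold at the 8.4.7 thresholds that operates whatever the cause.

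**Step 3. Dosing visits before the next scheduled scan**

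Inputs: chemistry and dosing on Day 1 of each 3-week cycle (Section 1.3); imaging every 12 weeks ±7 days during treatment (Section 1.2). Take an event first found at Week *w*, with the Week 12 scan still to come. Count the visit at which it is found as a dosing visit if it precedes the scan.

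- Scan at Week 12, before that day's dose: *n* = (12 − *w*)/3.
- Scan at Week 13, after the Week 12 dose: *n* = (12 − *w*)/3 + 1.

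| Event found at Week | 3 | 6 | 9 | 12 | Mean if equally likely |
|---|---|---|---|---|---|
| Nominal scan | 3 | 2 | 1 | 0 | (3+2+1+0)/4 = 1.5 |
| Late scan | 4 | 3 | 2 | 1 | (4+3+2+1)/4 = 2.5 |

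Equal likelihood across the four visits is an assumption. The pattern repeats for later 12-week intervals on treatment.

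**The case against.** The strongest reply is that the exposed case is narrow. An investigator who suspects recurrence would be expected to scan. Section 4.1 has recurrence documented radiographically, Section 8.2.1 provides expedited BICR once radiographic recurrence is identified, and verified recurrence ends treatment under Section 7.1. To be exposed, a participant needs an investigator who blames progression, orders no scan, does not hold and keeps dosing. Physicians judge causality throughout the protocol, and the safeguards in Step 2 and eDMC safety review remain. All of this stands as a limit on frequency. It does not supply the missing requirement, because each safeguard is discretionary, later, or tied to the class from which the event has been removed.

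A reader might also infer that Section 8.4.7 and Table 6 give opposite defaults for an event of uncertain cause, since one requires a judgement that progression is not the cause and the other exempts only events judged to be caused by it. The documents do not establish that conflict. Table 6 is a reporting table whose row starts from hepatic ECIs, a class defined in Section 8.4.7, so it does not bring in an event that Section 8.4.7 leaves out. Both texts presume that the investigator has made a judgement. The three wordings should be harmonised, but as a drafting repair.

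A third inference would be that a compulsory hepatic work-up is lost. Section 6.6.2 words the evaluation more softly: "All participants should be considered for evaluation according to the directions below within 72 hours of the alert for a non-overdose ECI".

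**Conclusion.** The point holds as an inexpensive patient-safety improvement. An unverified attribution to progression is enough to remove the required hold and the 24-hour ECI notice, and the treatment default in that state is to continue. The gap is confined to attribution without verified recurrence.

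The 0 to 3 dosing visits (1 to 4 with a late scan) are a worst-case calendar count that assumes no unscheduled scan and no voluntary hold. They do not measure risk. The documents give no rate of misattribution, so no number of affected participants can be stated.

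A reader might infer bias in the safety comparison between arms. The documents do not support that: no planned between-arm comparison rests on hepatic ECI counts. Nor can it be said that the hepatic stops in Section 7.1 are switched off. That list differs from Section 8.4.7 (for example, it includes a Child-Pugh score above 9), and its ALT item carries no limit on cause.

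**What to change.** In Section 8.4.7 and Table 6, replace the three exclusions with one sentence:

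> *Every event meeting the thresholds is a hepatic ECI, including when the cause is uncertain or recurrence is only suspected, and requires holding study treatment and Sponsor notification within 24 hours, unless BICR-verified or pathology-confirmed recurrence is present and is judged by the investigator to explain the event.*

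Add to Section 8.2.1, so that the hold and the continue-treatment default do not collide:

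> *A hepatic ECI hold applies while verification of recurrence is pending; if recurrence is not verified, restart follows Section 6.6.2.*

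Investigator judgement is kept, but it can exempt an event only once recurrence has been verified. A marked ALT rise in a participant with a verified extrahepatic node, for instance, would stay a hepatic ECI unless that recurrence explains it.

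Two CRF fields are optional: whether the investigator attributes the event to recurrence, and whether and when recurrence was verified or confirmed.

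The cost is two sentences of text, plus some extra 24-hour reports and temporary holds for events that prove to be recurrence.
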